## 7.1.2 Screening

All patients will be adults. If they are being recruited into tier 2, they must be able to provide written informed consent. Patients who cannot read or write or have cognitive impairment will not be included.

## 7.1.3 Payment

No payments will be made to participants.

## 7.2 Consent (Tier 2)

This is required for tier 2 only. Participants will be approached by the local VERN and COVER investigator to provide written informed consent. The Principal Investigator (PI) retains overall responsibility for the conduct of research at their site; this includes the taking of informed consent of

participants at their site. They must ensure that any person delegated responsibility to participate in the informed consent process is duly authorised, trained and competent.

Informed consent will be obtained prior to the participant having any data recorded in Tier 2. The right of a participant to refuse participation without giving reasons will be respected.

The participant will be free to withdraw at any time from the study without giving reasons and without prejudicing his/her further treatment and will be provided with a contact point where he/she may obtain further information about the study. Data collected up to the point of withdrawal will only be used after withdrawal if the participant has consented for this. Where a participant is required to re-consent or new information is required to be provided to a participant it is the responsibility of the PI to ensure this is done in a timely manner.

Patients who cannot read or write or have cognitive impairment will not be included. Participants will be given a PIS prior to signing a consent form and will have the opportunity to ask questions.

A capable person will:

- 1. understand the purpose and nature of the research
- 2. understand what the research involves, its benefits (or lack of benefits), risks and burdens
- 3. understand the alternatives to taking part
- 4. be able to retain the information long enough to make an effective decision
- 5. be able to make a free choice
- 6. be capable of making this particular decision at the time it needs to be made (though their capacity may fluctuate, and they may be capable of making some decisions but not others depending on their complexity).

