## Tier 2 - Vascular and endovascular procedural data capture

## **Primary objective**

This tier of the project is aimed at capturing data on all vascular and endovascular interventions being undertaken throughout the COVID-19 pandemic. It is anticipated that the type and nature of vascular procedures performed will change due to the pressures on the wider healthcare service and rationing of resources or in-patient beds.

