#### **Outcomes**

## **Primary outcome:**

To document all vascular surgery and interventional procedures performed throughout the COVID-19 pandemic across participating centres; during this stage we will only collect the name of the procedure performed, time and date, with intra-operative details; no patient-specific information will be collected as part of this.

Specifically, we will collect the following information using a remote purpose built data collection form (per centre/patient):

- Type of procedure performed
- Time taken from presentation to the surgical team to intervention
- Mode of referral (primary vs. secondary care)
- Site of surgery hub or spoke hospital
- Imaging modalities used and timings
- Emergency classification i.e. urgent/emergency/elective
- Operative technique(s) and device(s) used
- Mode(s) of anaesthesia (local, regional, general, locoregional, other)
- Whether suspected or confirmed COVID-19 positive (+ve) at time of surgery, COVID-19 +ve after surgery, or COVID-19 negative (-ve)

• Documentation of changes to usual practice for this specific procedure as per surgeon's standard protocol (type of procedure, type of anaesthetic, post-procedural destination)

These **secondary outcomes** will be collected after surgery has been performed at 3, 6, and 12 months:

- Re-admission
- Re-intervention
- All-cause mortality
- Operation-specific morbidity
- Morbidity
- [If COVID-19 +ve] respiratory outcome, admission to intensive care unit.

Each centre will assign a unique patient-specific and study-specific number to each procedure/patient (kept in local site files in the NHS institutions) and then this information will be collected locally three and six months after surgery has taken place. This will be uploaded anonymised on the data collection tool.

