#### 7.1.1 Patient identification

Patients will be identified daily via conversation with the on call registrar and consultant for vascular surgery.

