#### 12. ETHICAL AND REGULATORY CONSIDERATIONS

#### 12.1 Ethical approval and research governance

The study will be conducted in compliance with the principles of the ICH GCP guidelines and in accordance with all applicable regulatory guidance, including, but not limited to, the UK policy framework for health and social care research. Ethical approval for this study will be sought from the Research Ethics Committee combined with Health Research Authority (HRA) approval. No study activities will commence until favourable ethical opinion and HRA approval has been obtained. Progress reports and a final report at the conclusion of the trial will be submitted to the approving REC within the timelines defined by the

committee. Confirmation of capacity and capability will be obtained from the R&D department prior to commencement of the study at all participating sites.

Successful ethical approval for the UK was granted on the 2nd of April 2020 (Rec Reference: 20/NW/0196 Liverpool Central) for study Tiers 2 and 3. HRA approval was granted on the 3rd of April 2020. The approval mandates patient consent for tier 2 in order to capture procedural data and follow-up. Tier 3 was deemed not to require specific consent from the participant as often these are based on referred information and there is likely to be no direct patient contact.

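### Tier 2 sets out to document every procedure but records only patients who gave their own prior written consent, so its counts fall short by construction and no denominator is specified

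*Protocol*

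**What the plan says.** **Target.** The Tier 2 primary objective in section 7 is "capturing data on all vascular and endovascular interventions being undertaken throughout the COVID-19 pandemic". The Tier 2 primary outcome repeats this: "To document all vascular surgery and interventional procedures performed throughout the COVID-19 pandemic across participating centres". The Study Summary makes the types of procedure performed the outcome measure for the study's primary objective. Section 8.3 reports the absolute number of patients having each procedure, and the proportion dying or having an amputation at 3, 6 and 12 months.

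**Entry rules.** Section 7.2: "Informed consent will be obtained prior to the participant having any data recorded in Tier 2". Section 7.1.2: "If they are being recruited into tier 2, they must be able to provide written informed consent", followed by "Patients who cannot read or write or have cognitive impairment will not be included". Section 7.2 adds: "The right of a participant to refuse participation without giving reasons will be respected". Section 12.1 shows that consent was not a free choice: "The approval mandates patient consent for tier 2 in order to capture procedural data and follow-up".

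**Identification.** Section 7.1.1 gives one route: "Patients will be identified daily via conversation with the on call registrar and consultant for vascular surgery". The opening of section 7 gives two points for Tiers 2 and 3: when surgery takes place, and on referral to the on-call team.

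**The concern.** The stated target is a census of procedures, but the entry rules produce a consented sample. A reader of the results would take the absolute numbers as the activity of the participating centres, when they are the activity in patients who were approached, able to consent and willing.

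The loss is unlikely to be random. Section 6.1 includes stroke and aneurysmal disease, and the Tier 2 form records whether a case is emergency, urgent or elective. Capacity, and survival to the point of consent, plausibly vary with both diagnosis and urgency. The reported procedure mix and urgency split could therefore differ from the true ones, and not only the totals. Section 1 says that the study is meant to inform planning of future vascular care, so the counts matter in their own right.

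The protocol describes no tally of eligible procedures against which the shortfall could be seen. Section 8.4 deals with missing items for patients already entered, not with patients who were never entered.

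**Working it through.** The plan gives no figure to reproduce. Section 8.1 says that no sample size calculation could be done, and the protocol states neither a consent rate nor a mortality rate. The check is therefore a comparison of passages followed by simple algebra.

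**Step 1: who can have a Tier 2 record.**

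| Patient having a procedure | Tier 2 record? | Source |
|---|---|---|
| Consents before or after surgery | Yes, from consent onward | 7.2 |
| Refuses | No | 7.2 |
| Cannot read or write, or cognitively impaired | No | 7.1.2, 7.2 |
| Temporarily too unwell, later recovers capacity | Yes, if then consented | 7.2 |
| Never regains capacity | No; no consultee or other route is described | 7.1.2, 7.2 |
| Dies before consent | No | 7.2 |
| Withdraws | Earlier data used only if the patient agreed to this | 7.2 |

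Section 12.1 applies the consent requirement to procedural data as well as to follow-up, so a procedure cannot be counted under one rule and followed up under another.

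**Step 2: counts.** If N procedures are eligible and a share f cannot be recorded, the Tier 2 count is N(1 − f). This is below N whenever f > 0, whatever the outcomes of the missing patients. For assumed f of 5%, 10%, 20% and 30%, capture is 95%, 90%, 80% and 70%. None of these values of f comes from the protocol.

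**Step 3: mortality.** Let m0 be mortality in recorded patients and m1 mortality in those lost. All-procedure mortality is (1 − f)·m0 + f·m1. The observed value is m0, so the error is m0 − [(1 − f)·m0 + f·m1] = f·(m0 − m1).

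- If m1 = m0, the error is zero.
- If m1 > m0, mortality is understated; if m1 < m0, it is overstated.
- Patients who die before consent are all deaths, so that component of the loss can only lower the observed proportion. For patients who refuse, or who cannot read or write, the protocol gives no reason to expect either direction.

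To show how far any figure depends on its inputs, take m0 = 5% and f from 5% to 30%, all assumed:

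| Assumed m1 | Understatement, percentage points |
|---|---|
| 5% | 0 throughout |
| 20% | 0.05 × 15 = 0.75, up to 0.30 × 15 = 4.5 |
| 40% | 0.05 × 35 = 1.75, up to 0.30 × 35 = 10.5 |

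The answer runs from nothing to more than ten points on inputs that the protocol does not supply, so no size can be claimed.

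**Step 4: identification.** Section 7.1.1 names only the on-call conversation, whereas the opening of section 7 also provides for identification at surgery. Elective and interventional procedures are in scope for Tier 2, yet neither passage names theatre or interventional radiology lists as a source. The two passages are unreconciled, but they do not amount to an on-call-only rule.

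**The case against.** The case on the other side is substantial, and several parts of it stand.

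- **Consent is mandated.** Section 12.1 makes it a condition of approval, so the requirement itself is not a design error. This stands, and the fix leaves it in place.
- **Consent precedes recording, not surgery.** Section 7.2 also recognises that capacity may fluctuate, so an emergency patient can be consented on recovery. This stands. The loss is limited to patients who refuse, meet the exclusion, never regain capacity or die first.
- **Tier 3 needs no consent.** It asks for a proforma on every referred patient with limb-threatening ischaemia, symptomatic carotid disease, acute aortic syndrome or aneurysmal disease, and follows mortality to one year. It will catch many of the urgent cases. It does not give Tier 2 a denominator, because it covers referrals for listed conditions over a minimum of one month, while Tier 2 covers all procedures over three months in the first instance.
- **Mortality is secondary in Tier 2**, section 8.3 does not assign its death and amputation proportions to a tier, and no comparisons are planned. This stands, and the point therefore rests on the counts.
- **A screening log may exist.** The Schedule of Events has a screening column with an eligibility assessment, and a log could sit in site files. That is possible, but the protocol neither requires a count of procedures not included nor plans to report one.

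A reader might also infer that on-call identification removes many elective or radiology cases. The opening of section 7 contradicts that reading, and the documents give no basis for saying how many would be missed.

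**Conclusion.** The point holds on the counts and rests on the protocol's own text. Tier 2 cannot document all procedures under its entry rules, and section 8.3 would present a consented subset as absolute numbers with no stated denominator. The shortfall is f. It is above zero as soon as one eligible patient is not consented, but its value is unknown.

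On mortality the conclusion is conditional. Tier 2 mortality is probably understated if patients lost to consent die more often, which is plausible for emergencies without capacity. A reader might go further and treat a downward bias of a particular size as established. The documents do not support this: they give no consent rate and no mortality in either group, and equal mortality would mean no bias.

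On identification the finding is that two passages need to be reconciled. This is an inexpensive correction to a descriptive cohort, and it does not undermine the design.

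**What to change.** 1. **Keep** written consent for all patient-level Tier 2 data.
2. **Add a denominator.** Each centre keeps an anonymous aggregate count of eligible procedures by type and urgency, with the number included and the number not included by reason (refused, lacked capacity or met the exclusion, died before approach, missed). The sponsor and REC should first confirm that this count needs no consent, since section 12.1 ties consent to capturing procedural data.
3. **Report coverage.** In section 8.3, give Tier 2 counts together with the capture fraction by procedure type and urgency. In the Tier 2 outcomes and section 8.3, label patient-level results as outcomes among consented patients.
4. **Reconcile identification.** Align section 7.1.1 with the opening of section 7, so that theatre and interventional radiology lists are used as well as the on-call conversation.
5. **Confine the exclusion.** State in section 7.1.2 that the literacy and cognition exclusion applies to Tier 2 only. Section 7.2 repeats it under a Tier 2 heading, but as worded in 7.1.2 it could be applied to Tier 3, which needs no consent.

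The cost is edits to a few sections, a query to the sponsor and REC, and a short routine log check by existing collaborators. The count has to be kept while recruitment runs, because procedures not logged at the time cannot be recovered by a later analysis plan.

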## 7.3 Storage and analysis of samples

No samples will be stored or analysed.

## 7.4 End of study definition

12 months after the inclusion of the last patient i.e. 12 months after the last recruited patient has taken part.

#### 8. STATISTICS AND DATA ANALYSIS

## 8.1 Sample size calculation

This is an observational study and given the unique nature of this unforeseen pandemic we cannot perform sample size calculations.

#### 8.2 Planned recruitment rate

We expect one to five participants per centre per week.

## 8.3 Statistical analysis plan

We will report absolute numbers of patients having each procedure during this observational study period. We will report proportion of patients dying or having amputation at 3, 6, and 12 months. No comparisons will be made.

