## **STUDY SUMMARY**

Full title		The impact of COVID-19 pandemic on the provision, practice and outcomes of vascular surgery			
Short title	COVER	COVER			
Aim	Assess the impact of COVII	Assess the impact of COVID-19 on vascular surgery			
Design	Multicentre Cohort Study	Multicentre Cohort Study			
Participants	•	All patients with a vascular pathology idenfied and treated during the COVID-19 pandemic			
Sample size	200 participants - ESTIMAT	200 participants - ESTIMATED			
Planned project period	24 months - ESTIMATED	24 months - ESTIMATED			
	Objectives	Outcome Measures			
Primary	Assess how the COVID-19 pandemic has changed the provision of vascular services in the UK	Collect data regarding the types of procedures performed in vascular units.			
Secondary	Assess how the COVID-19	Collect data regarding			

Key Words: Coronavirus, Cohort study, Outcomes, Vascular, Surgery

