## Tier 1 - Changes to vascular unit level clinical processes

## **Primary objective**

To objectively capture the changes made to the structure and delivery of vascular surgery at unit level throughout the COVID-19 pandemic, and compare it to the guidance provided by the VSGBI as well as other national/international committees (e.g. the Society for Vascular Surgery, the European Society for Vascular Surgery).

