#### **Methods**

The Tier 1 "service evaluation study" will be circulated to all interested centres and data collected (remotely/online) at the start of COVER. The aim is to identify changes to the routine or standard vascular service structure. This will be conducted at roll-out and upon each centre registering to participate in the overall study bundle. This survey will be repeated at regular intervals to document ongoing changes, in response to the changing circumstances. These intervals will vary depending on how the pandemic progresses internationally. Collaborators will be updated at least once weekly. It is expected that the responses will reflect the unit practice as a whole and should therefore be a unified unit level response approved by the centre or centre lead.

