## Tier 3 - Changes to acute vascular care management

## **Primary objective**

To identify how the management of all referred urgent vascular cases changes throughout the COVID-19 pandemic. This is to identify the many anticipated deviations from pre-pandemic best practice or pre-defined standards for acute/urgent cases due to healthcare pressures. This will focus on chronic limb-threatening ischaemia, symptomatic carotid disease, acute aortic syndromes and aneurysmal disease.

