## Abdominal Aortic Aneurysm (AAA)

- Increasing use of Endovascular repair (if applicable)
- Changes to criteria for intervention
- Decisions for palliation, i.e. 'turn down'

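### Section 8.3 rules out all comparisons, while the overall, Tier 1 and Tier 3 objectives require them; the two must be reconciled

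*Protocol*

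**What the plan says.** Section 8.3 contains two planned summaries and one rule. The summaries are "We will report absolute numbers of patients having each procedure during this observational study period" and "We will report proportion of patients dying or having amputation at 3, 6, and 12 months". The rule is "No comparisons will be made". Nothing restricts the rule to a tier, an outcome or a type of comparison. Section 3.1 also lists no comparison group.

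The objectives are set out in several places:

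- Study Summary, primary objective: "Assess how the COVID-19 pandemic has changed the provision of vascular services in the UK".
- Section 3.1: evaluate the pandemic's impact on vascular practice and its effect on patient outcomes.
- Section 7, Tier 1, primary objective: record unit-level changes and "compare it to the guidance provided by the VSGBI as well as other national/international committees".
- Section 7, Tier 2, primary objective: record the interventions carried out.
- Section 7, Tier 3, primary objective: "To identify how the management of all referred urgent vascular cases changes throughout the COVID-19 pandemic", including departures from earlier best practice or from standards fixed in advance. The aneurysm items under its primary outcome include "Increasing use of Endovascular repair (if applicable".

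**The concern.** Words such as changed, increasing, deviation and effect each need a reference level. That may be an earlier period, a guideline, a written standard or another group. Section 8.3 excludes all of them, and Tier 1 uses the very verb that Section 8.3 forbids.

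The investigators are then left with two poor choices. They can keep to Section 8.3 and leave several stated objectives without an analysis. Or they can make comparisons anyway, chosen after the data are in and contrary to the protocol. The second choice is the greater risk to credibility, because the periods, standards and outcomes compared could be picked by what they show.

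**Working it through.** No arithmetic applies. The protocol gives no effect size, baseline rate or power, Section 8.1 says no sample size calculation is possible, and the Study Summary gives 200 participants as an estimate only. The check is to set each objective beside what Section 8.3 permits.

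| Objective | What it needs | What Section 8.3 permits | Result |
|---|---|---|---|
| Study Summary: what has changed in provision | A reference period or standard | Totals over one period | Size of change not obtainable |
| Section 3.1: effect on outcomes | An outcome level without the pandemic | Pandemic-only proportions at 3, 6 and 12 months | Effect not obtainable |
| Tier 1: changes against guidance | Concordance with each guidance item | No comparison | Direct contradiction, if Section 8.3 covers Tier 1 |
| Tier 2: record procedures | Counts by procedure | Counts by procedure | Matched |
| Tier 3: how management changes, and departures from standards | A split by time and a named standard | No comparison | Not quantified |
| Tier 3, aneurysm: rising endovascular use | At least two periods, or a reference share | One total | Cannot be shown |

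Next, what the study collects that bears on change:

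1. Tier 1 surveys are repeated through the pandemic (Tier 1, Methods).
2. Tier 2 records the date and urgency of each procedure, and whether it differed from the surgeon's usual practice (Tier 2, Outcomes).
3. Tier 3 records departures from best practice patient by patient (Tier 3, Outcomes).

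So most of the raw material for descriptive comparisons within the pandemic exists. The obstacle is the sentence in Section 8.3. A pre-pandemic group is not among the data described, so an effect on outcomes stays out of reach whatever Section 8.3 says.

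Two features limit how Tier 2 counts can be read. First, the Tier 1 survey is tied to centre registration: "This will be conducted at roll-out and upon each centre registering to participate in the overall study bundle". This implies that centres enter at different times, so a count by period depends partly on how many centres are open. Second, Sections 7.1.2 and 7.2 require written consent before any Tier 2 data are recorded, and exclude people with cognitive impairment or who cannot read or write. Even a count per centre-week therefore reflects recruitment as well as surgical activity.

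**The case against.** **The unseen statistical analysis plan may settle this.** If detail were merely absent, that would be a full answer. Here the protocol states a prohibition without qualification, and a later plan that added comparisons would contradict it.

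**Section 8.3 may mean only that there is no between-group comparison.** Read with the absence of a comparison group in Section 3.1, this is plausible. The text does not say so, and under this reading the effect on outcomes still has no reference level.

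**Section 8.3 may not govern Tier 1.** It speaks of patients and procedures, and Section 4 says Tier 1 is not research. This may be the intention. It would remove the most literal clash but leave those with the Study Summary, Section 3.1 and Tier 3.

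**Change is itself a recorded variable.** This stands. A reader might infer that the study can say nothing about change. That goes too far: repeated surveys, reported changes to usual practice and recorded deviations can be summarised in a single group and partly describe what changed.

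**Counts suit some of the aims.** This also stands. A reader might infer that every primary objective is a contrast, or that Section 8.3 reports counts alone. Neither is so: the Tier 2 objective is data capture, and Section 8.3 also reports proportions at three time points.

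**Could the counts show a trend of the wrong sign?** A reader might build an example with assumed figures: 10 centres × 4 per week = 40, later 30 centres × 2 per week = 60. The total rises by 50% while the rate per centre falls by 50%. Both rates lie within the one to five per week of Section 8.2, but the centre numbers and the fall are assumed, and Section 8.3 plans period totals, not weekly counts. At 40 to 60 per week the estimated 200 participants would also be reached in 200/60 = 3.3 to 200/40 = 5 weeks, so the example fits the stated size poorly. It shows only that any count split by period needs a centre-time denominator.

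**Conclusion.** The contradiction is real and lies in the current text. Section 8.3 forbids what Tier 1 and Tier 3 set out to do and what the Study Summary and Section 3.1 promise. Followed as written, the study can describe procedures, crude outcomes and, in part, reported changes. It cannot quantify change over time or adherence to guidance, and it cannot show an effect on outcomes.

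The size cannot be put as a number, because no planned estimate is wrong; what is lost is the answer to several stated objectives. A purely descriptive cohort is a legitimate design, and if that is what the sponsor wants, the fault lies in the wording of the objectives. The conclusion assumes that Section 8.3 applies to all tiers, as its unrestricted wording implies. If Tier 1 is exempt, the point narrows to the overall and Tier 3 objectives and still holds.

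**What to change.** Replace the last sentence of Section 8.3 with named descriptive comparisons, each with a 95% confidence interval:

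1. **Tier 1:** the proportion of centre returns concordant with each listed guidance item, by survey round, with the number of centres replying in each round.
2. **Tier 2:** the procedure and urgency mix, and the recorded changes to usual practice, by calendar period. Give any count per participating centre-week, and label it as consented, recruited cases rather than total activity.
3. **Tier 3:** for each condition, the proportion of referrals deviating from the stated standard, by calendar period. Name the standard for each condition in advance, and confirm that the proforma carries a referral date, since the protocol does not list one.

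Fix the calendar periods before analysis. Tier 2 is planned for 3 months at first and Tier 3 for at least one month, so the periods may have to be short. A regression model for time trend is optional; the essential step is consistency.

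Because there is no pre-pandemic group, reword the outcome part of Section 3.1 to describing outcomes during the pandemic.

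If the sponsor wants description only, keep Section 8.3 and reword the objectives in the Study Summary, Section 3.1, Tier 1 and Tier 3, including the aneurysm item on rising endovascular use.

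The cost is a protocol amendment and a little more analysis on data largely collected already. Time trends must be labelled as associations within the pandemic, and may be imprecise at about 200 participants.
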